8.5.4 Analysis of exploratory endpoint(s)

All exploratory analyses below will be performed on the FAS only.

8.5.4.1 Trabecular Bone Score (TBS)

Changes from baseline in the TBS score at each visit during the treatment period will be analysed using ANCOVA in the same manner as the change from baseline in Tr.vBMD (radius) on HRpQCT (see Section 8.5.2.1).

8.5.4.2 Auditory Function

The audiometry score (Undetectable hearing loss, mild, moderate or severe) at each visit will be summarised descriptively by ear and treatment group.

8.5.4.3 Bone formation

Changes in baseline in the below bone formation parameters at each visit will be analysed using ANCOVA in the same manner as the change from baseline in Tr.vBMD (radius) on HRpQCT (see Section 8.5.2.1):

- Normalised newly mineralised bone volume (MV/BV)
- Normalised newly mineralised surface area (MS/BS)
- Mineralised thickness (MTh)
- Normalised formation patch number density (N.F. Patch/BV)
- Formation patch volume (F.PatchVol.)
- 3D bone formation rate (3D BFR/BS)
- 3D mineral apposition rate (3D MAR)

8.5.4.4 Bone Resorption

Changes in baseline in the below bone resorption parameters at each visit will be analysed using ANCOVA in the same manner as the change from baseline in Tr.vBMD (radius) on HRpQCT (see Section 8.5.2.1):

- Normalised newly eroded bone volume (EV/BV)
- Normalised newly eroded surface area (ES/BS)
- Erosion depth (ED)

- Normalised resorption cavity number density (N.R.Cav./BV)
- Resorption cavity volume (R.Cav.Vol.)
- 3D bone resorption rate (3D BRR/BS)
- 3D mineral apposition rates (3D MRR)

8.5.4.5 Follow-up Period Subgroup Analysis

A subgroup analysis (descriptive statistics and associated ANCOVA analyses) will be performed for HRpQCT, DXA, vertebral radiograph, CTX-1, and P1NP parameters at all follow-up visits by the administration of zoledronic acid during the follow-up period (none; at Month 12; at Month 18).

8.6 Safety analyses

All definitions relative to safety endpoints are detailed in [Section 7.1.4](#).

All the safety analyses will be based on the Safety population and will be performed for all safety variables specified below.

No statistical testing will be performed.

8.6.1 Adverse events

All AEs will be classified by SOC and PT according to the MedDRA Version 21.1 or higher.

Details for imputing missing or partial start dates of adverse events are described in Section **Error! Reference source not found.**

All AE summaries will be generated by treatment period, follow-up period and overall (i.e including those that started in both the treatment period and follow-up period).

Notes:

- Two AEs with the same PT and classified in the same category (pre-treatment AE or TEAE) will be considered as two different events when calculating the “number of events” in the tables.
- Where a patient has the same AE, based on preferred terminology, reported multiple times in the same category (pre-treatment AE or TEAE), the patient will only be counted once at the preferred terminology level in AE frequency tables.
- Where a patient has multiple AEs within the same SOC in the same category (pre-treatment AE or TEAE), the patient will only be counted once at the SOC level in AE frequency tables.
- AEs where the intensity is missing will be assumed to be “Severe”
- AEs where the causality is missing will be assumed to have “Reasonable possibility of relatedness”

An overall summary of AEs will be provided. The total number of events and number and proportion of patients experiencing any AEs, TEAEs, AEs related to study medication, SAEs, SAEs related to study medication, severe AEs, AEs leading to permanent discontinuation of study treatment and AEs leading to death will be tabulated for each treatment group and overall.

Additionally, TEAEs, related TEAEs, serious TEAEs, related SAEs, severe TEAEs, AEs leading to permanent discontinuation of study treatment and AEs leading to death will be summarised by SOC and PT for each treatment group and overall (number and percentage of patients experiencing at least one AE per PT as well as the number of observed events per PT). All TEAEs will also be summarised separately by maximum severity grade for each SOC and PT and by relationship to study medication for each SOC and PT.

The frequency and incidence of TEAEs will be presented by system organ class and preferred term for each treatment group (number and percentage of participants experiencing at least 1 AE per preferred term as well as the number of observed events per preferred term).

Infusion site reactions will be tabulated and summarised by treatment group and overall.

All AE tables will be presented on both the pooled and the non-pooled version of the Safety population.

All AEs will be presented in full in a comprehensive listing including patient number, treatment regimen, intensity, seriousness, actions taken, outcome, causality, onset/stop and duration. Details of all TEAEs of special interest, SAEs, AEs leading to permanent discontinuation of study treatment and AEs leading to death will be listed separately.

8.6.1.1 Adverse Events of Special Interest

The AESIs for setrusumab are:

- Fractures
- Cardiovascular events

The frequency and incidence of all treatment emergent AESIs will be presented by system organ class and preferred term for each treatment group.

8.6.2 Clinical laboratory evaluations

Haematology, blood chemistry and urinalysis assessment will be conducted at Screening, Baseline, Months 1, 2, 3, 6, 9 and 12/EOT during the treatment period and months 14, 18 and 24 during the follow-up period.

Clinical laboratory data will be reported in Standard International (SI) units. Descriptive statistics will be presented for quantitative laboratory parameters for each treatment group and time-point. Similarly, changes from Baseline will be summarised.

Values outside the normal range will be categorised as H (above the normal range) or L (below the normal range) based on the laboratory's reference range and these will be flagged in the individual data listings.

Line graphs of mean calcium values (+/- SE) and change from baseline in calcium (+/- SE) will be presented.

Serum pregnancy test results and Follicle-stimulating hormone and estradiol assessments recorded at screening will be listed only.

8.6.2.1 Liver Function

The number and proportion of patients with laboratory values for liver function and enzymes of clinical concern as follows will be presented descriptively by treatment group:

Parameter	Level for clinical concern
ALT	> 1.5 times the upper limit of the normal range (ULN) > 2xULN > 3xULN > 5xULN > 10xULN
AST	> 1.5xULN > 2xULN > 3xULN > 5xULN > 10xULN
Bilirubin Total	> 2xULN > 3xULN
ALT/AST and Bilirubin Total	ALT/AST > 3xULN and Bilirubin Total > 2xULN (assessments to occur at the same visit)

8.6.3 Vital signs

Vital signs will be performed at each planned visit during the treatment period and at months 14, 18 and 24 during the follow-up period.

Descriptive statistics (observed values and changes from baseline) will be presented for each treatment group and time-point for vital sign measurements (body temperature, respiratory rate (RR), pulse rate, systolic blood pressure, diastolic blood pressure, weight and BMI).

A data listing of vital signs for patients will be provided.

8.6.4 Physical examinations

All physical examination data and abnormalities will be listed by patient and body system.

8.6.5 Electrocardiograms

Single 12-lead ECG will be obtained at Screening, Months 6 and 12/EOT during the treatment period and Month 14 during the follow-up using an ECG machine that automatically calculates the heart rate (HR) and measures PR, QRS, QT and QTc intervals.

Descriptive statistics will be presented for the 12-lead ECG measurements for each treatment group and time-point. Similarly, changes from baseline will be summarised.

In addition, the overall ECG interpretation will be summarised by presenting the number and percentage of patients with “Normal”, “Abnormal, NCS” and “Abnormal, CS” for each treatment group and time-point.

A data listing of all ECG measurements will be provided.

8.6.6 Health Economics

The number of patients that required hospitalisation during the treatment period and follow-up period will be summarised descriptively. In addition the duration of hospitalisation, the unit to which the patient was admitted and the reason for hospitalisation during will be summarised descriptively by treatment group.

8.7 Other analysis

8.7.1 PK

Setrusumab concentrations will be summarised on the PK population by descriptive statistics by treatment group and time-point, and including the geometric mean and coefficient of variation.

A graphical representation of the setrusumab concentrations distribution using mean plots (mean and SD) will be provided over time per setrusumab dose-level on the PK population. All 3 dose-levels will be plotted on the same graph.

8.7.2 DMC

An independent, unblinded external DMC will periodically review accumulating safety data. This will include data evaluation of accumulating unblinded safety data of Setrusumab. Full details of composition, operational aspects, and data to be reviewed and recommendation of the DMC is provided in a separate DMC charter and DMC SAP.

8.7.3 Interim Analysis

There is no formal interim analysis planned, however the primary efficacy analysis and study unblinding will be performed when all data up to Month 12 has been collected. Given the study has

been powered at Month 12 and there will not be multiple comparisons, there is no requirement to adjust the Type I error rate.

Due to hierarchical nature of the primary end-point, the complexity of the data and timelines involved, Mereo has implemented a two-stage data transfer into the study database for the primary analysis. The initial transfer will include the majority of study data analysis including a lock and transfer of the clinical database and transfer of the primary end-point Tb. vBMD, the second transfer will include finite analysis (FEA) data from the HRpQCT, audited PK data and ADA data.

An analysis and unblinding of Sponsor will be completed on the first dataset – at this point the database will be locked and no further data manipulation will be completed. The vendors completing the data analysis for the second transfer will remain blinded to patient treatment allocation by nature that this information is retained at ICON Plc– additionally the FEA is a computed model process and the PK and ADA a fully validated assay which cannot be influenced by any full or partial unblinding. The data transfers will be completed into the clinical database with no further data manipulation for the existing data.

The Clinical Study report (CSR) will be prepared based upon the results of the primary analysis.

8.7.4 Follow-up Analysis

The data collected during the off treatment follow-up will be separately analysed and published in an addendum to the CSR.

9 CHANGES TO PLANNED ANALYSIS FROM PROTOCOL

Not applicable.

11 APPENDICES

Appendix A – SF12

The calculation of the SF12 V2.0 norm-based domain and component score is a 3 step process:

- 1) Reverse score / recalibrate item scores
- 2) Compute transformed raw scale domain scores (0-100)
- 3) Convert transformed raw scale domain scores to norm-based domain/component scores

Step 1: Reverse Score / Recalibrate Item Scores

Question 1: In General, Would you say your health is:

Response to Question 1	Scoring
Excellent	5.0
Very Good	4.4
Good	3.4
Fair	2.0
Poor	1.0

Question 2: Does your health limit you in:

- a) Moderate activities, such as moving a table, pushing a vacuum cleaner, bowling or playing golf
- b) Climbing several flights of stairs

Response to Question 2a/2b	Scoring
No, not limited at all	3.0
Yes, limited a little	2.0
Yes, limited a lot	1.0

Question 3: How much of the time have you had any of the following result of your physical health:

- a) Accomplished less than you would like
- b) Were limited in the kind of work or other activities

Response to Question 3a/3b	Scoring
None of the time	5.0
A little of the time	4.0
Some of the time	3.0

Most of the time	2.0
All of the time	1.0

Question 4: How much of the time have you had any of the following problems with your work or other regular daily activities as a result of any emotional problems:

- a) Accomplished less than you would like
- b) Were limited in the kind of work or other activities

Response to Question 4a/4b	Scoring
None of the time	5.0
A little of the time	4.0
Some of the time	3.0
Most of the time	2.0
All of the time	1.0

Question 5: How much did pain interfere with your normal work:

Response to Question 5	Scoring*
Not at all	5.0
A little bit	4.0
Moderately	3.0
Quite a bit	2.0
Extremely	1.0

* Scores are reversed from reported numeric values

Question 6: How much of the time during the past 4 weeks:

- a) Have you felt calm and peaceful
- b) Did you have a lot of energy
- c) Have you felt downhearted and depressed

Response to Question	6a/6b Scoring*	6c Scoring
None of the time	1.0	5.0
A little of the time	2.0	4.0

Some of the time	3.0	3.0
Most of the time	4.0	2/0
All of the time	5.0	1.0

* Scores are reversed from reported numeric values

Question 7: How much of the time has your physical health or emotional problems interfered with your social activities:

Response to Question 7	Scoring*
None of the time	5.0
A little of the time	4.0
Some of the time	3.0
Most of the time	2.0
All of the time	1.0

Step 2: Compute transformed raw scale scores

The 8 domain raw scale scores are calculated by first summing the responses for all items in that particular domain (see below table), then converting the score to a transformed 0-100 scale using the below formula:

SF-12v2 Scale	Sum items	Lowest, highest possible raw scores	Possible raw score range
Physical Functioning (PF)	2a,2b	2,6	4
Role Physical (RP)	3a,3b	2,10	8
Bodily Pain (BP)	5	1,5	4
General Health (GH)	1	1,5	4
Vitality (VT)	6b	1,5	4
Social Functioning (SF)	7	1,5	4
Role Emotional (RE)	4a,4b	2,10	8
Mental Health (MH)	6a,6c	2,10	8

$$\text{Transformed Scale} = \frac{\text{Actual raw summed score} - \text{lowest possible raw score}}{\text{Possible raw score range}} * 100$$

Step 3: Convert transformed raw scale domain scores to norm-based domain scores

To convert the transformed raw scale domain scores (as per step 2) to norm domain scores:

- 1) Firstly Z-scores for each domain must be calculated using the formulas below (based upon 1998 general US population):

$$\text{PF}_Z = (\text{PF} - 81.18122) / 29.10558$$

$$\text{RP}_Z = (\text{RP} - 80.52856) / 27.13526$$

$$\text{BP}_Z = (\text{BP} - 81.74015) / 24.53019$$

$$\text{GH}_Z = (\text{GH} - 72.19795) / 23.19041$$

$$\text{VT}_Z = (\text{VT} - 55.59090) / 24.84380$$

$$\text{SF}_Z = (\text{SF} - 83.73973) / 24.75775$$

$$\text{RE}_Z = (\text{RE} - 86.41051) / 22.35543$$

$$\text{MH}_Z = (\text{MH} - 70.18217) / 20.50597$$

$$\text{PCS}_Z = (\text{PF}_Z * 0.42402) + (\text{RP}_Z * 0.35119) + (\text{BP}_Z * 0.31754) + (\text{GH}_Z * 0.24954) + (\text{VT}_Z * 0.02877) + (\text{SF}_Z * -0.00753) + (\text{RE}_Z * -0.19206) + (\text{MH}_Z * -0.22069)$$

$$\text{MCS}_Z = (\text{PF}_Z * -0.22999) + (\text{RP}_Z * -0.12329) + (\text{BP}_Z * -0.09731) + (\text{GH}_Z * -0.1571) + (\text{VT}_Z * 0.23534) + (\text{SF}_Z * 0.26876) + (\text{RE}_Z * 0.43407) + (\text{MH}_Z * 0.48581)$$

- 2) Secondly norm-based scores are calculated by multiplying each Z-score by 10 and adding the resulting product to 50
e.g for Norm-Based PF = 50 + (PF_Z * 10)

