8.5.3.8.1 SF-12

Changes from baseline in the norm-based 8 domains scores and 2 component score of the SF-12 at each visit during the treatment period will be analysed using ANCOVA in the same manner as the change from baseline in Tr.vBMD (radius) on HRpQCT (see Section 8.5.2.1).

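### The General Health weight in the SAP's SF-12 mental component formula (-0.1571) appears to have lost a zero and to be ten times too large

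*SAP*

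**What the plan says.** SAP section 7.1.3.4 sends the reader to Appendix A for SF-12 scoring. Step 3 there standardises each domain, for example "GH}_Z = (\text{GH} - 72.19795) / 23.19041", forms the physical and mental component Z-scores as weighted sums, and rescales each as 50 + 10 × Z.

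The physical component weights are "PF}_Z * 0.42402) + (\text{RP}_Z * 0.35119) + (\text{BP}_Z * 0.31754) + (\text{GH}_Z * 0.24954" followed by "VT}_Z * 0.02877) + (\text{SF}_Z * -0.00753) + (\text{RE}_Z * -0.19206) + (\text{MH}_Z * -0.22069". The mental component weights begin "PF}_Z * -0.22999) + (\text{RP}_Z * -0.12329) + (\text{BP}_Z * -0.09731", continue with "GH}_Z * -0.1571) + (\text{VT}_Z * 0.23534", and end "SF}_Z * 0.26876) + (\text{RE}_Z * 0.43407) + (\text{MH}_Z * 0.48581".

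SAP section 8.5.3.8.1 analyses the result by ANCOVA: "Changes from baseline in the norm-based 8 domains scores and 2 component score of the SF-12 at each visit". Section 8.5.3.8 places that analysis on the FAS and the Non-restricted FAS. SF-12 change is a secondary endpoint (SAP section 4.2, item 18; Protocol section 5).

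The SAP cites no source for the weights; its reference list contains only ICH E9. Appendix B works through an EQ-5D-5L example, but Appendix A has none for the SF-12.

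**The concern.** Fifteen of the 16 component weights have five decimals; the GH weight in the mental component has four. A suppressed trailing zero is an unlikely explanation, because the appendix keeps trailing zeros elsewhere: "VT}_Z = (\text{VT} - 55.59090) / 24.84380". The value is also out of sequence with its neighbours. The natural reading is that -0.01571 was typed without its first zero.

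A tenfold weight would not cancel in change from baseline, since the error is proportional to each patient's change in GH. If a dose improves self-rated health, part of that improvement is subtracted from its MCS. If doses differ in their effect on GH, the comparison between doses is distorted as well. The score would also no longer be on the norm-based scale that the SAP describes. Independent double programming would not reveal this, because both programmers would code the same printed formula.

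**Working it through.** **Inputs.** All are from SAP Appendix A. Step 3 gives the weights, GH mean 72.19795, GH SD 23.19041 and the rescaling 50 + 10 × Z. Step 1 scores Question 1 as 1, 2, 3.4, 4.4 and 5; Step 2 turns these into GH = 0, 25, 60, 85 and 100. The SAP gives no worked MCS, so there is no stated result to reproduce.

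**1. Order and sums of the weights**

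| | PF | RP | BP | GH | VT | SF | RE | MH |
|---|---|---|---|---|---|---|---|---|
| Physical | 0.42402 | 0.35119 | 0.31754 | 0.24954 | 0.02877 | -0.00753 | -0.19206 | -0.22069 |
| Mental | -0.22999 | -0.12329 | -0.09731 | **-0.1571** | 0.23534 | 0.26876 | 0.43407 | 0.48581 |

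The physical weights fall at every step. The mental weights rise at every step except at GH; -0.01571 restores the order. The physical weights sum to 0.95078. The seven other mental weights sum to 0.97339, so the mental total is 0.97339 - 0.1571 = 0.81629 as printed and 0.97339 - 0.01571 = 0.95768 with -0.01571.

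**2. Internal consistency.** Assumption, not stated in the SAP: the weights are principal-component score coefficients after varimax rotation with Kaiser normalisation. Let B be the 8 × 2 matrix of weights.

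- Loadings are L = B(B'B)⁻¹. Each row is divided by the square root of its communality to give (x₁, x₂).
- Put u = x₁² - x₂² and v = 2x₁x₂. The residual rotation φ satisfies tan 4φ = 2(Σuv - ΣuΣv/8) / [Σ(u² - v²) - ((Σu)² - (Σv)²)/8]. A varimax solution requires φ = 0.
- With -0.1571, φ = -3.27 degrees. GH has communality 0.25 while every other domain is at 0.69 or above.
- Solving φ = 0 for the GH weight over -1 to 1, from the other 15 weights, gives three roots: -0.28972, -0.015713 and 0.55248. The first implies communalities of 1.01 and 1.05 and the last 1.16, which are impossible. The one admissible root rounds to -0.01571.
- With -0.01571, φ = 0.00001 degrees and all communalities lie between 0.63 and 0.78.
- Sensitivity: with -0.01571 in place, re-solving any one of the 16 weights from the other 15 returns it to five decimals. This is not separate evidence, but it shows that the condition is sharp enough to fix the digits. With -0.1571 in place, no weight is recovered.

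**3. Effect on individual scores.** GH_Z = (GH - 72.19795)/23.19041, and the GH contribution to MCS is 10 × weight × GH_Z.

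| Answer | GH | GH_Z | Printed weight | -0.01571 | Error |
|---|---|---|---|---|---|
| Poor | 0 | -3.113 | +4.89 | +0.49 | +4.40 |
| Fair | 25 | -2.035 | +3.20 | +0.32 | +2.88 |
| Good | 60 | -0.526 | +0.83 | +0.08 | +0.74 |
| Very good | 85 | +0.552 | -0.87 | -0.09 | -0.78 |
| Excellent | 100 | +1.199 | -1.88 | -0.19 | -1.70 |

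Fair to Good is 35/23.19041 = 1.509 SD, so MCS changes by -2.37 as printed against -0.24, an error of -2.13. Poor to Good gives -4.06 against -0.41. Over the full GH range MCS falls by 6.77 points as printed and by 0.68 with -0.01571; the largest error in a change score is 6.10. As printed, GH outweighs role-physical (-4.54 over its full range) and bodily pain (-3.97).

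**4. Effect on group means.** The error per GH point is 10 × (-0.1571 + 0.01571)/23.19041 = -0.061 MCS points. For illustrative mean GH gains (assumed, not from the documents) of 5 and 10 points, the error is -0.30 and -0.61.

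**The case against.** The documents do not contain -0.01571. They state no rule that the weights must run in order or that the two sums should agree, so those patterns are only suggestive. The consistency solution depends on an unstated scoring model, including Kaiser normalisation: without normalisation the roots are -0.181 and -0.021, and -0.01571 leaves a residual of 0.12 degrees. A zero could also have been lost when the PDF was converted to text.

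These points justify a check against the source. They do not rescue the printed value. All the other weights and all the norm constants came through with five decimals, and recovering the digits 1571 with one zero inserted is very hard to attribute to chance.

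On consequences, three points stand. A negative GH weight is not itself wrong: PF, RP and BP are also negative, and -0.01571 would still lower MCS slightly. The direction of bias depends on whether GH improves or worsens, and gains in VT, SF, RE or MH could offset it. The largest figures describe individual category jumps; errors in group means would usually be fractions of a point.

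**Conclusion.** The concern holds. The printed weight is inconsistent with the rest of its own formula, and -0.01571 is the value the other 15 weights support, assuming Kaiser-normalised varimax scoring. The exact replacement needs confirming from the scoring source. Programmed as written, the SAP would mis-score MCS by +4.40 to -1.70 points per patient and distort change scores by up to 6.10 points, or about 0.06 points per point of mean GH change. The bias runs against the drug if GH improves on treatment and in its favour if GH worsens.

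The scope is narrow: one of the two SF-12 summary scores, within a secondary endpoint that has no multiplicity adjustment. It should be corrected, but it does not bear on the primary conclusion.

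**What to change.** Check all eight mental component weights against the SF-12v2 scoring source and the signed SAP. Replace the GH weight with the confirmed five-decimal value (expected -0.01571) and cite the source in Appendix A. In the same pass, correct the 2/0 printed for 2.0 in the Question 6 table.

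Before programming is signed off, run two test records through both the program and the source algorithm. With -0.01571, all domains at 100 should give MCS 62.39 (60.70 under the printed weight), and all domains at 0 should give 16.04 (20.45 under the printed weight).

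The cost is one coefficient and one validation check. No data collection or other analysis changes.
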